6.2.2 Descriptive analyses

Summary statistics will be provided by treatment group and visit for total number of colony forming units, all spirometry parameters (FEV1, FVC and FEV1/FVC ratio) and HRCT parameters including regional and global air tapping changes will include arithmetic mean, standard deviation (SD), coefficient of variation (CV), median, minimum and maximum. These will be calculated at all time points as specified in the assessment schedule (Table 8-1) of CSP and specifically at the primary time point of interest (Day 84) considering placebo as the reference treatment.

Summary statistics will be provided by treatment group and visit for Cough and Sputum Assessment Questionnaire (CASA-Q) and St. George's Respiratory Questionnaire (SGRQ) domain scores, COPD assessment test (CAT), EQ-5D-3L and EXACT-PRO questionnaire data.

6.3 Statistical model, assumptions and hypotheses

The secondary objective analysis will include all available data from subjects in the PD analysis set.

The change from baseline in the logarithm of the total number of colony forming units including all different micro-organisms (\log_{10} CFU) and change from baseline in the secondary efficacy including global air trapping and spirometry parameter will be analyzed using the same model (MMRM) as for the primary variable of interest. Contrasts for treatment differences will be provided together with two-sided 80% Confidence Intervals.

Similarly, other secondary pharmacodynamics and efficacy endpoints (CASA-Q, SGRQ, CAT, EQ-5d-3L and EXACT-PRO) will be analyzed using the same model (MMRM) as for the primary variable of interest.

The following analyses will be performed to explore any differences in the exacerbation events that occur in QBW251 vs placebo:

1. Time to first exacerbation

The time-to-event analyses will be carried out only upon sufficient number of exacerbation events occur during the study to estimate the median in either of the treatment groups.

The time to the first on-treatment exacerbation (event) is defined as the start date of first exacerbation minus the date of randomization +1. Subjects who do not experience an exacerbation or discontinued earlier without an exacerbation will be censored for analyses purposes.

Novartis	Confidential	Page 15 of 20
SAP Amendment 1		Study No. CQBW251B2202

The hazard ratios for QBW251 compared with placebo and their corresponding 80% confidence intervals will be computed using Kaplan-Meier method. The stratification factor may include number of exacerbations in the last 12 months as ≤ 1 and ≥ 1 .

The Kaplan-Meier estimates of the survival functions for each treatment will be plotted.

A Cox proportional hazards regression model will be applied in time-to-event analyses to test the null-hypothesis H0: λ QBW251(t) / λ Placebo(t) = 1, where λ (t) is the hazard function for the failure time of subjects treated with QBW251 dose and Placebo, respectively.

The Cox regression model will be stratified by number of exacerbations in the last 12 months. The SAS procedure PROC PHREG will be used for analysis. Results will be presented with adjusted hazard ratios for treatment group comparisons and associated 80% confidence intervals. No check for the validity of proportional hazards assumptions will be done.

2. Annualized rate of COPD exacerbations

The total frequency of COPD exacerbations over the 12-week treatment period will be analyzed using a generalized linear model assuming a negative binomial distribution.

The time at risk for a subject is defined as the length of time the subject is on treatment and the log (length of time) will be used as the offset variable in the model. The model will include treatment, antibiotic use, and the number of exacerbations in the past 12 months prior to screening as categorical variables. An estimate of the rate ratio together with 80% confidence intervals and corresponding p-value will be presented.

3. The percentage of subjects experiencing at least a COPD exacerbation

The proportion of subjects with at least one COPD exacerbation will be analyzed using logistic regression. The model will include treatment, antibiotic use, and the number of exacerbations in the past 12 months prior to screening as categorical variables. The estimated odds ratios will be displayed along with the associated 80% confidence intervals.

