#### 8.4.4 COPD Exacerbation

Symptom-defined COPD exacerbations identified by the EXACT-PRO instrument (EXACT-PRO-defined exacerbations) are defined as a persistent increase from baseline in total EXACT-PRO score of ≥9 points for 3 days or ≥12 points for 2 days. Whenever the EXACT-PRO diary data suggest that the subject symptoms are worsening according to the above definitions, the diary will trigger an alert advising the subject to contact the site.

A healthcare resource utilization (HCRU)-defined exacerbation is defined as an acute worsening of respiratory symptoms (consisting of at least two of the following symptoms: dyspnea, cough, sputum volume, sputum purulence, chest tightness or wheeze) that requires a change in treatment. HCRU exacerbations are defined as moderate if leading to treatment with systemic glucocorticosteroids and/or antibiotics, and as severe if leading to hospital admission or emergency room (ER) visit lasting >24 h in addition to treatment with systemic glucocorticosteroids and/or antibiotics. Mild HCRU exacerbations are events that can be managed with an increase in usual medication and without the addition of systemic therapy.

Exacerbation therapy is at the discretion of investigators. Suggested therapy includes 5 days of oral prednisolone (or equivalent) 40 mg/day and/or an oral 7 day course of amoxicillin 500 mg t.i.d. (alternatively amoxicillin/clavulanic acid 625 mg t.i.d. or clarithromycin 500 mg b.i.d.) (GOLD 2018).

Subjects who develop a COPD exacerbation between screening and prior to treatment will be screen failed but will be permitted to be re-screened after a minimum of 2 weeks after exacerbation SOC therapy has been stopped. (see Section 5). Scheduled spirometry should not be performed during an exacerbation until it has completely resolved, therefore any scheduled visits that include spirometric assessment should be postponed until the subject has recovered. Visits that do not include spirometric assessment can go ahead as planned. Of note, budesonide and fluticasone are sensitive substrates of CYP3A. Where administered systemically for a COPD exacerbation, efficacy and safety of these drugs should be carefully monitored (see also Section 6.2 for further details).

In case of exacerbation alerts, subjects will need to visit the Site as soon as reasonably possible and be assessed to confirm the exacerbation. This visit will be considered as an unscheduled visit.

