## 12.5.2 Safety endpoints

For all safety analyses, the safety set will be used. All listings and tables will be presented by treatment group.

Safety summaries (tables, figures) include only data from the on-treatment period with the exception of baseline data which will also be summarized where appropriate (e.g. change from baseline summaries). In addition, a separate summary for death including on treatment and post treatment deaths will be provided. In particular, summary tables for adverse events (AEs) will summarize only on-treatment events, with a start date during the on-treatment period (treatment-emergent AEs).

The on-treatment period lasts from the date of first administration of study treatment to 1 week after the last actual administration of any study treatment.

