# 1) Time to first exacerbation

The time-to-event analyses will be carried out only upon sufficient number of exacerbation events occur during the study to estimate the median in either of the treatment groups.

The time to the first on-treatment exacerbation (event) is defined as the start date of first exacerbation minus the date of randomization +1. Subjects who do not experience an exacerbation or discontinued earlier without an exacerbation will be censored for analyses purposes.

The hazard ratios for QBW251 compared with placebo and their corresponding 80% confidence intervals will be computed using Kaplan-Meier method. The stratification factor may include number of exacerbations.

The Kaplan-Meier estimates of the survival functions for each treatment will be plotted.

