1.4 Study design and treatment

This is a randomized, subject and investigator blinded, parallel-group, placebo-controlled study investigating the mode of action (MoA) and preliminary efficacy and safety of QBW251 administered orally twice daily (b.i.d.) for 12 weeks in subjects with moderate to very severe COPD (GOLD 2-4). Approximately 100 subjects will be randomized in a 1:1 ratio to either QBW251 or placebo. Based on the assumption of a 15% drop-out rate (% drop out based on completed proof-of-concept COPD study CQBW251X2201), it is expected to have approximately 84 subjects to complete the study. Interim analysis plans were discontinued with strategic decision to stop this trial prior to completion.

The study consists of the following periods (Figure 1-1) : Screening, Baseline / Day 1, Treatment, and End of the Study followed by an additional post-treatment safety phone call. The total duration for each subject in the study is up to approximately 19 weeks.

Figure 1-1 Study design

Commercially Confidential Information

Therefore, CQBW251B2202 study drug dose arms are:

- QBW251 CCI
- Placebo b.i.d

2 First interpretable results (FIR)

First interpretable results (FIR) will be provided for this trial. Commercially Confidential Information

3 Interim analyses

Commercially Confidential Information

4 Statistical methods: Analysis sets

For all analysis sets, subjects will be analyzed according to the study treatment(s) received.

No screen failure data will be presented.

The safety analysis set will include all subjects that received any study drug.

The pharmacokinetic (PK) analysis set will include all subjects with at least one available valid (i.e. not flagged for exclusion) PK concentration measurement, who received QBW251 and experienced no protocol deviations with relevant impact on PK data.

The pharmacodynamic (PD) analysis set will include all subjects with PD data at both baseline and at least one post-baseline assessment which are not affected by any protocol deviations.

The analysis sets and protocol deviation codes are related as follows:

Table 4-1		
Category Text description of deviation Deviation code		Data exclusion
Subjects are PDs:	e excluded from Safety analysis in case of these	Exclude subject from Safety analysis set
INCL01	Informed consent was not obtained before any assessment	Y

 Table 4-1
 Protocol deviation codes and analysis sets

Novartis	Confidential	Page 10 of 20
SAP Amendment 1		Study No. CQBW251B2202

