All ECG data will be listed by treatment group, subject and visit/time, abnormalities will be flagged. Summary statistics will be provided by treatment and visit/time.

Clinical laboratory evaluations

All laboratory data will be listed by treatment group, subject, and visit/time and if normal ranges are available, abnormalities will be flagged. A separate listing is provided presenting all parameters in a subject with any abnormal values. Summary statistics will be provided by treatment and visit/time. Shift tables using the low/normal/high (low and high) classification will be used to compare baseline to the worst on-treatment value.

Adverse events

All information obtained on adverse events will be displayed by treatment group and subject.

Summary tables for adverse events (AEs) will summarize only on-treatment events, with a start date during the on-treatment period (treatment-emergent AEs).

The on-treatment period lasts from the date of first administration of study treatment to 1 week after the last actual administration of any study treatment.

The number (and percentage) of subjects with treatment emergent adverse events (events started after the first dose of study medication or events present prior to start of double-blind treatment but increased in severity based on preferred term) will be summarized in the following ways:

- by treatment, primary system organ class and preferred term.
- by treatment, primary system organ class, preferred term and maximum severity.
- by treatment, Standardized MedDRA Query (SMQ) and preferred term.

Separate summaries will be provided for study medication related adverse events, death, serious adverse events, other significant adverse events leading to discontinuation.

A subject with multiple adverse events within a primary system organ class is only counted once towards the total of the primary system organ class.

Listings will be provided for all AEs, SAEs and fatal AEs.

Novartis	Confidential	Page 19 of 20
SAP Amendment 1		Study No. CQBW251B2202

For the legal requirements of ClinicalTrials.gov and EudraCT, two required tables on treatment emergent adverse events which are not serious adverse events with an incidence greater than 5% and on-treatment emergent serious adverse events and SAE suspected to be related to study treatment will be provided by system organ class and preferred term on the safety set population.

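### The time-to-first-exacerbation analysis runs only if a median can be estimated, although neither the Cox hazard ratio nor the Kaplan-Meier curves need one

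*SAP*

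**What the plan says.** Time to first COPD exacerbation is a listed secondary endpoint (Protocol Table 2-1, SAP Table 1-1).

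- **The condition.** SAP 6.3, item 1, opens with "The time-to-event analyses will be carried out only upon sufficient number of exacerbation events occur during the study to estimate the median in either" arm. Protocol 12.5.4 also allows the analysis "only upon sufficient number of exacerbation events occur during the study to estimate the median in either of the treatment groups".
- **What it covers.** Both documents then call for hazard ratios with 80% confidence intervals and a Kaplan-Meier plot. The SAP adds the model: "A Cox proportional hazards regression model will be applied in time-to-event analyses to test the null-hypothesis" of equal hazards. The Cox model is therefore one of the conditional analyses. The protocol item names no Cox model.
- **What is left open.** No median is listed as an output, no event count is set, and nothing says what is reported if the condition fails.
- **What is not conditional.** The negative binomial rate model and the logistic model for the proportion with an exacerbation (items 2 and 3) carry no such rule.
- **The window.** Item 1 counts on-treatment events without defining the term. The explicit definition is in the safety sections: "The on-treatment period lasts from the date of first administration of study treatment to 1 week after the last actual administration" (SAP 7.2), and likewise "to 1 week after the last actual administration of any study treatment" (Protocol 12.5.2).

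**The concern.** The condition does not match what is to be reported. A Cox model needs events and risk sets, and a Kaplan-Meier curve can be drawn wherever it ends. Only the median itself needs a curve to fall to 0.5.

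Three things follow:

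- At lower event rates a listed secondary comparison disappears, although an estimate with an honest interval was available.
- The decision to run the comparison is taken arm by arm on the outcome being compared. Results that do appear are a selected set, and their error rate is no longer the nominal one. For the same placebo rate, a drug that prevents exacerbations also makes the analysis less likely to run.
- *Either* can mean at least one arm or both arms. Two programmers could reach opposite decisions on the same data.

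**Working it through.** **Inputs from the documents.** About 100 randomised 1:1, so 50 per arm; 15% drop-out; "it is expected to have approximately 84 subjects to complete the study" (SAP 1.4). The completer figure reproduces: 50 × 0.85 = 42.5, rounded down to 42 per arm, gives 84 (100 × 0.85 = 85 without rounding by arm). Treatment lasts 84 days; adding the safety sections' one week gives 91.

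**Assumed, because the documents do not give it.** The on-study rate of first events. Protocol 8.4.4 defines the EXACT-PRO event (a "persistent increase from baseline in total EXACT-PRO score of ≥9 points for 3 days", or a larger rise for 2 days) but states no rate, and the sample-size section is redacted. I use 2 to 4 per patient-year, constant and equal in both arms, with no drop-out. I take a median as reached when at least half of an arm has had an event.

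**Step 1: rate at which half an arm has an event.**
- 84 days: ln 2 / (84/365.25) = 3.01 per year
- 91 days: ln 2 / (91/365.25) = 2.78 per year

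**Step 2: chance that the condition is met.** p = 1 − exp(−rate × days/365.25); q = P(Binomial(n, p) ≥ n/2); at least one arm = 1 − (1 − q)²; both arms = q². Example at 3 per year, 84 days, n = 50: p = 0.498, q = 0.547, so 1 − 0.453² = 79% and 0.547² = 30%.

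**Step 3: two-sided error when the condition is met.** Exponential times with no treatment effect, unstratified log-rank test, |z| > 1.2816 (the 20% level that matches an 80% interval), by simulation.

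Results for 50 per arm, as chance met / error when met:

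| Rate per year | One arm, 84 d | One arm, 91 d | Both arms, 84 d | Both arms, 91 d |
|---|---|---|---|---|
| 2 | 8% / 63% | 15% / 52% | – | – |
| 2.5 | 40% / 36% | 58% / 30% | 5% / 2% | 12% / 3% |
| 3 | 79% / 25% | 91% / 22% | 30% / 6% | 49% / 8% |
| 3.5 | 97% / 21% | 99% / 20% | 66% / 10% | 82% / 14% |
| 4 | 99.7% / 20% | >99.9% / 20% | 89% / 16% | 96% / 18% |

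The rates at which the condition is met half the time are 2.6 (84 days) and 2.4 (91 days) per year for one arm, and 3.3 and 3.0 for both arms.

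With 42 per arm, one arm sufficing, 84 days, the condition is met in 11%, 44%, 80% and 96% of trials at 2, 2.5, 3 and 3.5 per year, with error when met of about 58%, 35%, 24% and 21%.

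**Step 4: drop-out and a real effect.** With 15% drop-out, 50 per arm and a placebo rate of 3 per year, the one-arm condition is met in 74% of trials under no effect and 52% at a hazard ratio of 0.7. Under the both-arms reading the figures are 24% and 2.7%.

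**Step 5: what an unconditional hazard ratio would show.** The 80% interval is the hazard ratio multiplied or divided by exp(1.2816 × 2/√events): 2.25 with 10 events in total, 1.77 with 20, 1.60 with 30 and 1.50 with 40.

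**The case against.** - **The conditional error can mislead.** A false positive counts only if the analysis also runs, so the condition cannot raise the trial-level error above the unconditional 20%. With one arm sufficing it is about 5%, 15%, 19% and 20% at 2, 2.5, 3 and 3.5 per year. This stands: the 63% figure describes the 8% of trials in which a result would be reported, not all trials. The SAP also sets no test level for the Cox model; 20% is inferred from the 80% interval.
- **The rate is unknown.** Diary-defined events may be frequent. At about 3.5 per year or more, with one arm sufficing, the condition is nearly always met and does no practical harm. This stands and limits what can be said about impact.
- **The objective is largely covered.** Two unconditional models address exacerbations, and Protocol 12 calls the study non-confirmatory. This lowers the weight but does not give the condition a purpose.
- **The percentages depend on conventions.** SAP 6.3, item 2, counts events over the 12-week treatment period, which favours the 84-day column. Requiring survival strictly below 0.5 (26 of 50) lowers the 84-day one-arm figures from 40% to 28% at 2.5 per year and from 79% to 68% at 3. The SAP's Cox model is stratified; the simulated test is not. The SAP also records a "strategic decision to stop this trial prior to completion", so the final sample size is not known. The percentages are illustrative; the mismatch between condition and outputs does not depend on them.
- **Sparse data can justify a rule.** True, but a median read arm by arm is the wrong criterion. The width of the interval already shows the imprecision.

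**Conclusion.** The concern holds. The condition is not technically needed for any output named in item 1, its wording has two readings, and following it can withhold a listed secondary comparison because of that comparison's own data. This rests on the text and the method, not on an assumed rate.

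The size does rest on the rate. Under the stated assumptions the effect runs from near-certain suppression below about 2 events per year to none at about 3.5 or more if one arm suffices. If both arms are required, suppression remains common at 3.5 per year over 84 days (34% of trials). When the analysis does run, its error is above nominal under the first reading at rates below about 3.5 per year, and below nominal under the second. The primary and key secondary analyses are untouched. The change should be made, but the trial's main conclusions do not turn on it.

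**What to change.** Delete the median condition. Always report the Cox hazard ratio with its 80% confidence interval and the Kaplan-Meier curves, and give the median only where it is reached, otherwise as not reached. If the team wants a sparse-data rule, set a minimum total event count, pooled over arms, before unblinding.

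Two small points can be settled in the same edit. Attribute the hazard ratio to the Cox model only, since the text also credits it to the Kaplan-Meier method. Check the strata for prior exacerbations, which as printed both include a count of one; this may be a conversion error, but if it is not, make them mutually exclusive before unblinding.

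The cost is a short SAP amendment before database lock. Changing Protocol 12.5.4 as well needs a formal amendment under Protocol 14.1; otherwise record the change in the SAP as a departure from the protocol. The downside is a wide interval when events are few.

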## Treatment period (from Day 1 to Day 84)

Once eligibility has been confirmed from Screening and Baseline assessments, subjects will be randomized in 1:1 ratio into one of the two treatment arms; placebo b.i.d. or QBW251 300 mg b.i.d.

The treatment period is 84 days in duration, with dosing twice daily. During this period, subjects will have to return to the site at Day 28, Day 56 and Day 84 for CCI blood/sputum sample collections, PK, safety, efficacy assessments, and eDiary check. At these visits, subjects will return all used and unused study medication and packaging. At Day 14, the site will call the subject to evaluate compliance and to check subject's wellbeing.

Pharmacokinetic blood sampling (pre and post-dose) will be done at Day 1, Day 28, Day 56 and Day 84 visits. Additionally, a subset of approximately 30-40 subjects will undergo pharmacokinetic serial sampling pre and up to 8 hours post-dose on Day 1 and on Day 28.

As a formal thorough QT assessment of QBW251 has not been completed, triplicate ECGs preand post-dose at Tmax will be performed at visits on Day 1, Day 28, Day 56 and Day 84 (end of treatment). These assessments will be complemented by PK sampling (trough and Cmax) on the matching time-points, at visits on Day 1, Day 28, Day 56 and Day 84.

A second HRCT will be performed at Day 84 after the morning dose of study medication at site. If the HRCT can't be performed at Day 84 for any reason, the exam needs to be planned within the 3 coming days and subject must continue to take study medication.

Subjects experiencing an exacerbation during the treatment period will continue with the study treatment along with the standard of care (SOC) therapy for a moderate exacerbation (i.e. antibiotic and/or systemic corticosteroids). Prior to the SOC therapy administration, subjects have to visit their study center for sputum sample collection in order to determine if there are changes in pathogen or bacterial load which may have resulted in the exacerbation.

Subjects with a severe exacerbation who need to be treated in the hospital will be discontinued of study treatment during this time with the possibility to restart study treatment 2 weeks after the last SOC therapy intake for the exacerbation.

End of treatment assessments will be performed at Day 84 visit.

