## 8.5.1.5 **Electronic Diary (eDiary)**

At Screening all subjects will be provided with an electronic diary (eDiary).

CCI eDiary will record background therapy and study drug medications intake (dose) after randomisation, as well as the study questionnaires (EXACT-PRO (daily), CAT, CASA-Q, SGRQ and EQ-5D-3L) at prespecified timepoints. Refer to SOM for details in different registration starting time-points (for background therapy, questionnaires, study drug intake).

Commercially Confidential Information

Starting from Day 1, subjects will be required to complete the EXACT-PRO questionnaire daily as well (see Section 8.5.1.4 for EXACT-PRO questionnaire). The eDiary is to be reviewed at each clinic visit until study completion.

Sites and subjects will receive appropriate training and guidance on the use of the eDiary device. A list of eDiary questions is provided in SOM.

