As a consequence, investigational study drug must be permanently discontinued in a subject exhibiting

- an estimated AUC0-24h > 91,700 ng\*hr/ml in association with a reported SAE
- an estimated AUC0-24h > 159,000 ng\*hr/ml even in the absence of any SAE (please see more details regarding this topic on Section 6.5.1.1).

If a female subject of childbearing potential withdraws from the study prematurely, the investigator should recommend her to maintain contraceptive measures for at least 3 days after the last dose of the study drug.

If permanent discontinuation of study treatment occurs, the investigator should make a reasonable effort to understand the primary reason for the subject's premature discontinuation of study treatment and record this information.

The investigator must also contact the IRT to register the subject's discontinuation from study treatment.

If discontinuation occurs because treatment code has been broken, please refer to Emergency breaking of treatment code Section 6.6.3.

Subjects who have their study treatment permanently discontinued should NOT be considered withdrawn from the study UNLESS they withdraw their consent (see withdraw of informed consent section). Where possible, they should return for the assessments indicated in the

assessment schedule in Table 8-1. If they fail to return for these assessments for unknown reasons, every effort (e.g. telephone, e-mail, letter) should be made to contact the subject/predesignated contact as specified in the lost to follow-up section. This contact should preferably be done according to the study visit schedule. If the subject cannot or is unwilling to attend any visit(s), the site staff should maintain regular telephone contact with the subject, or with a person pre-designated by the subject. This telephone contact should preferably be done according to the study visit schedule and at a minimum information on new/ concomitant treatments and adverse events /serious adverse events should be obtained.

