# 2) Annualized rate of COPD exacerbations

The total frequency of COPD exacerbations over the 12 week treatment period will be analyzed using a generalized linear model assuming a negative binomial distribution. The time at risk for a subject is defined as the length of time the subject is on treatment and the log (length of time) will be used as the offset variable in the model. The model will include treatment, antibiotic use, and the number of exacerbations in the past 12 months prior to screening as categorical variables. An estimate of the rate ratio together with 80% confidence intervals and corresponding p-value will be presented.

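### The exacerbation-rate model counts events over the 84-day treatment period but takes only time on drug as time at risk, so events captured after stopping drug have no matching exposure.

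*SAP*

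**What the plan says.** **The count.** SAP 6.3 item 2: "The total frequency of COPD exacerbations over the 12-week treatment period will be analyzed" with a negative binomial model. Protocol 12.5.4 item 2 has the same rule: "The total frequency of COPD exacerbations over the 12 week treatment period will be analyzed using a generalized linear model". Protocol 3.1 fixes the length of that period: "The treatment period is 84 days in duration, with dosing twice daily".

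**The offset.** Both documents then narrow the exposure: "The time at risk for a subject is defined as the length of time the subject is on treatment". The log of that time is the offset.

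**Follow-up after stopping drug.** Protocol 9.1.1: "Subjects who have their study treatment permanently discontinued should NOT be considered withdrawn from the study UNLESS they withdraw their consent". It continues: "Where possible, they should return for the assessments indicated in the" assessment schedule. On the diary, Protocol 8.5.1.5 says: "The eDiary is to be reviewed at each clinic visit until study completion". Protocol 8.5.1.4 has EXACT-PRO completed daily.

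**The neighbouring analysis.** Item 1 of the same SAP section limits its endpoint to events on treatment: "The time to the first on-treatment exacerbation (event) is defined as the start date of first exacerbation minus the date of randomization +1". Item 2 has no such limit.

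**The only defined on-treatment window.** It runs from first dose to 1 week after last dose. It stands with the safety analyses (SAP 7.2, Protocol 12.5.2), and neither exacerbation analysis refers to it.

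**The concern.** A rate model with a log-time offset estimates events per unit of time only if the count and the time come from the same interval. Here the count window is a calendar window (Day 1 to Day 84) and the offset is an exposure window. They agree for a subject who takes drug for all 84 days, and for one who leaves the study on stopping drug. They disagree for a subject who stops drug early and is still observed. That subject's later exacerbations are counted, but the days on which they could occur are not.

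The annualised rate and the rate ratio are both at stake. Item 1 states an on-treatment restriction and item 2 does not, so two programmers following the SAP could also report different rates from the same data.

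**Working it through.** **1. The plan's only related figure.** SAP 1.4 and Protocol 3 expect about 84 completers from about 100 randomised with 15% drop-out. 100 × (1 − 0.15) = 85, and 84 / 0.85 = 98.8, so the figure reproduces to rounding. It describes drop-out from the study. The quantity needed here is the share who stop drug but stay under observation, and neither document gives it.

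**2. One subject.** Assume a constant event rate, drug stopped on day *s*, and observation to Day 84. The expected count covers 84 days and the offset covers *s* days, so the expected rate is inflated by 84/*s*:

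- Day 28: 84/28 = 3.0
- Day 42: 84/42 = 2.0
- Day 56: 84/56 = 1.5
- Day 70: 84/70 = 1.2

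**3. One arm.** If a share *q* stop on day *s* and stay, inflation = 84 / (84(1 − *q*) + *q*·*s*). For *q* = 15%:

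- *s* = 28: 84 / (71.4 + 4.2) = 84/75.6 = 1.11
- *s* = 42: 84 / (71.4 + 6.3) = 84/77.7 = 1.08
- *s* = 56: 84 / (71.4 + 8.4) = 84/79.8 = 1.05

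**4. Rate ratio when the true ratio is 1.0.** This is the QBW251 inflation divided by the placebo inflation.

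| Stopping, QBW251 v placebo | *s* = 28 | *s* = 42 | *s* = 56 |
|---|---|---|---|
| 15% v 15% | 1.00 | 1.00 | 1.00 |
| 20% v 10% | 78.4/72.8 = 1.08 | 79.8/75.6 = 1.06 | 81.2/78.4 = 1.04 |
| 25% v 5% | 81.2/70.0 = 1.16 | 81.9/73.5 = 1.11 | 82.6/77.0 = 1.07 |

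The last row is an extreme case, shown only to bound the effect.

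**5. Check in the planned type of model.** A negative binomial model with a log-time offset was fitted to simulated data: 200,000 subjects per arm, rate 1.5 per year, dispersion 0.5, stop days spread evenly over Days 7 to 84, true ratio 1. The model held treatment only.

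| Stopping | Quantity | As written | On-drug events over on-drug time | All events over observed time |
|---|---|---|---|---|
| 15% v 15% | Placebo rate (true 1.50) | 1.62 | 1.49 | 1.50 |
| 25% v 5% | Rate ratio (true 1.0) | 1.10 | 1.01 | 1.00 |

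Either way of matching the windows removes the bias.

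**6. Borrowing the safety window for the count alone does not help.** A subject who stops on Day 28 would have events counted for 28 + 7 = 35 days against 28 days of exposure, and 35/28 = 1.25.

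The stopping shares, stop days, event rate and dispersion in steps 2 to 5 are all assumptions, because the documents give none of them.

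**The case against.** The strongest reply is that the sponsor meant on-treatment events over on-treatment time. Item 2 refers to the treatment period, follows an item that is explicitly on-treatment, and defines risk time as time on treatment. On that reading nothing is mismatched. The reading is possible, but item 2 does not state it. Item 1 does, and the protocol gives the treatment period a fixed length. The one on-treatment window that is defined does not match the offset either.

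Four further points stand and limit the concern:

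- **Diary entry after stopping is inferred.** Return visits are made where possible. For subjects who do not attend, the stated minimum is telephone contact on treatments and adverse events. The rate endpoint is EXACT-PRO-defined, so with no diary entries there is no event to miscount.
- **Hospitalised exacerbations.** A reader might infer that an event shortens its own time at risk, because Protocol 8.4.4 suspends drug during hospital treatment. No text says that interruption days are subtracted, so the documents leave this open. The suspension also depends on severity defined by health care use, not on the EXACT-PRO definition.
- **Bias against QBW251.** A reader might infer this because drug concentrations are evaluated only in QBW251 subjects (Protocol 8.5.2), so the exposure-based stopping rules in 9.1.1 can act only in that arm. But Protocol 4.5 expects few subjects above the lower threshold, and stopping at that threshold also needs a serious adverse event. Nothing supports a particular difference between arms.
- **Precision is low.** On the inputs of step 5 with 50 per arm, 50 × 1.5 × 84/365.25 gives about 17 events per arm. The standard error of the log ratio is √(2 × (1/0.345 + 0.5)/50), about 0.37, so an 80% interval runs from the ratio divided by 1.6 to the ratio times 1.6. A shift to 1.08 is about 0.2 standard errors.

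**Conclusion.** The concern holds as a mismatch in the written rule. The count covers 84 days, the offset covers time on drug, and the protocol plans follow-up of subjects for whom the two differ. The annualised rate is inflated to the extent that those subjects are observed. The rate ratio is biased only if stopping differs between arms in frequency or timing.

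On assumed values the size is modest: about 5-11% on the rate with 15% stopping at Day 28-56 in both arms, and a ratio of about 1.04-1.08 instead of 1.0 with 20% v 10%. The documents do not support the stronger statements that both rates are certainly too high, or that the ratio will run against QBW251.

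This is one of several secondary endpoints in a study that the protocol calls non-confirmatory. The primary fibrinogen analysis is unaffected. The rule should still be corrected, because as written it can yield a wrong rate and the correction is small.

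**What to change.** In SAP 6.3 item 2 and Protocol 12.5.4 item 2, make count and offset cover the same interval. Choose one as the main analysis and run the other as supportive:

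- **(a) On treatment:** count exacerbations that start in a stated on-treatment window, with the log of the days in that same window as the offset. Reconcile the window with the safety definition (last dose plus 1 week), and use it for item 1 as well.
- **(b) Under observation:** count all exacerbations from Day 1 to Day 84 or study exit, if earlier, with the log of the days under observation as the offset.

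Under either option, state whether days of temporary drug interruption count as time at risk, since the documents are silent.

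The cost is a sentence or two in each document and one additional model run. Under (a), events after the window leave the main rate model, but they remain in the supportive run.
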